A complete physical exam will be conducted at screening. Any abnormal findings must be assessed and documented as not clinically significant if a subject is to be enrolled in the study. The investigator or qualified designee will conduct the exam, determine findings, and assess any abnormalities as to clinical significance.

Causal relationship to the study drug may be:

1. Not Related in which case a clinical event, including laboratory test abnormality, with a temporal relationship to drug administration which makes a causal relationship improbable, and/or in which other drugs, chemicals, or underlying disease provide plausible explanations.

2. Possible in which case a clinical event, including laboratory test abnormality, with a reasonable time sequence to administration of the drug, but which could also be explained by concurrent disease or other drugs or chemicals. Information on drug withdrawal may be lacking or unclear.

3. Probable in which case a clinical event, including laboratory test abnormality, with a reasonable time sequence to administration of the drug, unlikely to be attributed to concurrent disease or other drugs or chemicals, and which follows a clinically reasonable response on re-administration (rechallenge) or withdrawal.

Reporting of Serious Adverse Events (SAEs)

In the case of a serious adverse event (SAE), the investigator must contact the local IRB and the Sponsor by telephone or fax immediately (within 24 hours of awareness). Full details of the SAE should be recorded on the medical records, copies of which should be forwarded by fax to the local IRB and to the Sponsor (Veloxis).

The following minimum information is required: • Internal Study number, • Subject number, sex, and age, • Date of report, • Description of the SAE (event, seriousness of the event), and • Causal relationship to the study drug. All AEs occurring after informed consent is signed should be collected and recorded in the electronic chart. All new SAEs and Adverse Drug Reactions (non-serious and serious AEs related to systemic tacrolimus) will be captured and recorded in the medical record.

Follow-up of Adverse Events

All AEs occurring during the study are to be followed up until resolved or judged to be no longer clinically significant, or until they become chronic to the extent that they can be fully characterized. If during AE follow-up, the adverse event progresses to an "SAE", or if a subject experiences a new SAE, the investigator must immediately report the information to the Sponsor. Local IRB will inform the investigator that some events reported as SAEs may not require expedited reporting to the IRB. The Sponsor will monitor these events throughout the course of the study.

Version Date: 11Jun2019 13 of 16

Procedure in Case of Pregnancy

If a female subject or partner of a male subject becomes pregnant during the study dosing period or within 30 days from the discontinuation of dosing, the investigator should report the information as an SAE. The expected date of delivery or expected date of the end of the pregnancy, last menstruation, estimated conception date, pregnancy result and neonatal data etc., should be included in this information. The medical status of the mother, as well as the fetus, will be followed and outcome reported to the IRB.

DISCONTINUATION

Discontinuation is defined as a subject who enrolled in the study and for whom study treatment is permanently discontinued prematurely for any reason. The subject is free to withdraw from the study treatment and/or study for any reason and at any time without giving reason for doing so and without penalty or prejudice. The investigator is also free to terminate a subject's involvement in the study at any time if the subject's clinical condition warrants.

Discontinuation Criteria from Treatment for Individual Subjects:

- Subject develops allograft loss (death, re-transplantation, transplant nephrectomy, or return to dialysis ≥ 6 consecutive weeks);
- Subject develops unacceptable toxicity or is withdrawn at the discretion of the patient's supervising physician;
- Subject is lost to follow-up despite reasonable efforts by the investigator to locate the subject;
- Subject withdraws consent for further treatment or expires during the course of the study;
- Conversion to a non-tacrolimus-based maintenance regimen in either study arm if required to manage toxicities;

OPERATIONAL AND ADMINISTRATIVE CONSIDERATIONS

Data Collection

The investigator or site designee will enter data collected using the local Electronic Medical Record (EMR) systems. In the interest of collecting data in the most efficient manner, the investigator or site designee should record data, including local laboratory values, in the hospital visit form during hospital admissions including the transplant admission (Eclipsys EMR) or office visit form (Crown) within 5days after the subject visit. The investigator or site designee is responsible to ensure that all data in the EMR are recorded within 5 days of the visit. Source data will be available at the site in the two EMR (inpatient- Eclipsys and outpatient- Crown in the Allscript System). Source data will include the medical treatment and history of the subject. The following information will be included: • Demographic data (age, sex, race, ethnicity, height and body weight) • Cross-match results • Separate donor source data including donor demographics, KDPI of donor kidney and donor HLA typing • Participation in study and original signed and dated informed consent • Visit dates • Medical history and physical examination details • Adverse events(including causality) and concomitant medication • Results of relevant examinations when appropriate • Laboratory tests • Reason for premature discontinuation (if applicable) • Randomization number

Direct Access to Source Data/Documents

The investigator and the study site will provide assistance for any monitoring and auditing by Veloxis, as well as inspections from the IRB relevant regulatory authorities as requested. In these instances, the investigator or his designee will assist at the review of all study-related records, without allowing independent access to the records per the rules of

the hospital. The confidentiality of the subject's identities shall be well protected consistent with local and national regulations when the source documents are subject to inspection.

Protocol Deviations

A protocol deviation is generally an unplanned excursion from the protocol that is not implemented or intended as a systematic change. The investigator is responsible for ensuring the study is conducted in accordance with the procedures and evaluations described in this protocol and for protecting the rights, safety, and welfare of subjects. The investigator should not implement any deviation from, or changes to, the protocol, unless it is necessary to eliminate an immediate hazard to trial subjects. For the purposes of this protocol, deviations requiring notification to Sponsor and to the local IRB are defined as any subject who: • Entered into the study even though they did not satisfy entry criteria. • Received wrong treatment or incorrect dose. • Received excluded concomitant treatment. When a deviation from the protocol is identified, the investigator or designee must ensure that local IRB is notified.

Documents and Records Related to the Clinical Study

The investigator will archive all study data in the patient's electronic data chart (e.g., Subject Identification Code List, source data, and eGFR,) and relevant correspondence. Data generated by the methods described in the protocol will be recorded in the subjects' medical records and/or study progress notes.

Protocol Amendment and/or Revision

Any changes to the study that arise after approval of the protocol must be documented as protocol amendments. Depending on the nature of the amendment, either IRB approval or notification may be required. The changes will become effective only after the approval of Veloxis, the investigator, and the IRB. Amendments to this protocol must be signed by Veloxis and the investigator. Written verification of IRB approval will be obtained before any amendment is implemented which affects subject safety or the evaluation of safety, and/or efficacy. Modifications to the protocol that are administrative in nature do not require IRB, but will be submitted to the IRB for their information. If there are changes to the Informed Consent, written verification of IRB approval must be forwarded to Veloxis. An approved copy of the new Informed Consent must also be forwarded to Veloxis.

Schedule of Events

	Screening (-21 to Day 0)	Randomization	Transplant (Day 0)	Month 1 - Month $12 (\pm 2 \text{ weeks})^3$
Consent	Х			
Demographic	Х			
Medical History	Х			Х
Height and weight ¹	Х		Х	Х
Transplant information			Х	
Randomization Assignment ²		Х		
IP Dispensation			Х	Х
Clinical Laboratory assessment	Х			Х
Pregnancy test (WOCBP only)	X			X
Concomitant Medications	Х	Х	Х	Х
Adverse Events	Х	Х	Х	Х
Study drug accountability			Х	X

¹Height and Body Weight: Height and dry weight will be recorded at screening and pre-operatively on study day 0. ²For living donors, the randomization will happen at the pre-operation check-up at the hospital, which happens about 7 days before transplant operation. For deceased donors, the randomization will happen at admission for the transplant operation. ³Month 1 to Month 12 Visits will be conducted in conjunction with SOC visits. Adverse events and drug accountability will be reviewed for research purposes.

Version Date: 11Jun2019 16 of 16

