Official Title: To Understand the Impact of Immunosuppression Using Once-perday Envarsus XR on the Effect of Total Tacrolimus Dose/Trough Level Ratio on Renal Function (eGFR) in Kidney Transplantation

Unique Protocol ID: AAAR6805

Registration Identifier: NCT03511560

Document Date: June 11, 2019

Primary Objective: To compare the relationship of once daily tacrolimus extended release (Envarsus) versus twice daily tacrolimus immediate release (Prograf) doses to achieve target trough concentrations (C) relative to the total daily dose (D) given and the effect of C/D ratio on renal function at day 7 and months 1, 3, 6, and 12 months after transplantation utilizing concentration to dose ratio (C/D ratio).

Secondary Objective:

- Compare incidence of rejection between the groups at 90 and 365 days post-transplant (Banff grade I-III and antibody mediated rejection [AMR])
- Compare graft loss and death within 1 year post-transplant
- Death within 1 year post-transplant
- Compare and summarize serious adverse events (AEs) between study groups

Study Population: Living or deceased donor kidney transplant recipients 18 to 80 years of age.

Number of Subjects to be Enrolled / Randomized: 50 patients [25 patients in each arm]

Study Design Overview:

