This is a one year, prospective, randomized, open-label trial examining once versus twice daily tacrolimus dosing regimen using two preparations, Envarsus vs Prograf. It will examine kidney function between the two groups using eGFR and also examine one year kidney outcomes, including graft loss and patient death. Biopsy will be performed on clinical indications only (not protocol) when rejection or other problem is suspected in face of deteriorating renal function in each study group utilizing Banff criteria. Patients will be screened prior to surgery and randomized 1:1 to receive, within 48 hours of transplantation, immediate release tacrolimus, administered twice daily, or Envarsus, administered once daily as a component of a standard immunosuppression maintenance regimen also consisting of mycophenolate sodium (MPA) (or mycophenolate mofetil equivalent). Induction therapy will be given and administered per center protocol (rabbit anti-thymocyte globulin 6mg/kg over 4 days except in HLA identical living donor/recipient pairs when basiliximab induction is used intraoperatively). Intravenous corticosteroids (methylprednisolone 500mg intraoperatively with a daily rapid taper to 250, 125, 80 mg) over 4 days will be administered prior to rabbit antithymocyte globulin and prior to revascularization as part of the initial induction regimen. Thereafter, patients will be followed for up to 1 year during the open label study period. After discharge from the hospital, the patients randomized to immediate-release tacrolimus will be permitted to receive any immediate release tacrolimus product available to them through normal dispensing mechanisms. Envarsus will be supplied by Veloxis and dispensed by the research pharmacy.

Inclusion Criteria:

Subject is eligible for the study if all of the following apply:

1. Kidney transplant patient \ge 18 years and \le 80 years old

- 2. Institutional Review Board (IRB) approved written Informed Consent and privacy language must be obtained from the subject prior to any study-related procedures (including withdrawal of prohibited medication, if applicable).
- 3. Recipient of a *de novo* kidney from a living or deceased donor.
 - a. If deceased donor, a Kidney Donor Profile Index (KDPI) ≤ 85% are eligible for enrollment.
- 4. Willingness to comply with study protocol.

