- 5. Previous kidney transplants will be permitted. Patients who are receiving a secondary transplant and who previously received Envarsus or who are currently on Envarsus as a component of maintenance immunosuppression and re-listed for transplant will be eligible to enroll in this study and will be randomized at the time of transplant to either cohort.
- 6. Subject agrees not to participate in another study while on treatment.
- 7. Female subject must be either:
 - a. Of non-child-bearing potential,
 - i. Post-menopausal (defined as at least 1 year without any menses) prior to screening, or
 - ii. Documented surgically sterile or status post-hysterectomy
 - b. Or, if of childbearing potential,
 - i. Agree not to try to become pregnant during the study and for 90 days after the final study drug administration
 - ii. And have a negative serum or urine pregnancy test within 14 days prior to transplant procedure
 - iii. And, if heterosexually active, agree to consistently use two forms of highly effective birth control (at least one of which must be a barrier method) which includes consistent and correct usage of established oral contraception, established intrauterine device or intrauterine system, or barrier methods of contraception: condom or occlusive cap (diaphragm or cervical/vault caps) with spermicidal foam/gel/film/cream/suppository, starting at screening and throughout the study period and for 90 days after the final study drug administration.
- 8. Male subject and their female spouse/partners who are of childbearing potential must be using highly effective contraception consisting of two forms of birth control (one of which must be a barrier method) starting at screening and continuing throughout the study period and for 90 days after the final study drug administration).
- 9. Female subjects must agree to not breastfeed from screening through end of the study period.

Waivers to the inclusion criteria will NOT be allowed. Patients meeting inclusion criteria at the time of randomization and not initiated on Envarsus or immediate-release tacrolimus within 48 hours of transplant will be classified as a recruitment failure and not included in the analysis.

Exclusion Criteria:

Subject will be excluded from participation if any of the following apply:

- 1. Patient is known to have a positive test for latent tuberculosis (TB) and has not previously received adequate anti-microbial therapy or would require TB prophylaxis after transplant.

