Endpoints for Evaluation:

Primary: To compare the relationship of once daily tacrolimus extended release (Envarsus) versus twice daily tacrolimus immediate release (Prograf) doses to achieve target trough concentrations (C) relative to the total daily dose (D) given

and the effect of C/D ratio on renal function at day 7 and months 1, 3, 6, and 12 months after transplantation utilizing concentration to dose ratio (C/D ratio).

Secondary: Comparison between treatment cohorts regarding incidence will rely upon assessments for each of the following results:

- Compare incidence of rejection between the groups at 90 and 365 days post-transplant (Banff grade I-III and antibody mediated rejection [AMR])
- Compare graft loss and death within 1 year post-transplant
- Compare and summarize serious adverse events (AEs) between study groups
- Death within 1 year post-transplant

Statistical Analysis:

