Medical History: Etiology of renal failure, viral serology (HBV, HCV, CMV, EBV), and diabetes history (as applicable). *Transplant Information*: Day 0 visit: type of transplant (living related, living non-related, DD, and whether organ was obtained in the setting of DCD or CDC), number of prior transplants and reason for prior graft loss (if applicable), total cold and warm ischemia time in hours and minutes, KDPI, ABO blood typing, HLA typing of donor and recipient, degree of HLA mismatch between donor and recipient, and most recent panel reactive antibody testing. Donor viral serology information (HBV, HCV, CMV, EBV), if available, will be collected and recorded. Additional donor information includes age, sex, height, weight, donor cause of death, ethnicity, ABO typing, and results of any pre-implantation biopsies. *Height and Body Weight*: Height and dry weight will be recorded at screening and pre-operatively on study day 0.

Efficacy Assessment

Estimated Glomerular Filtration Rate: Estimated glomerular filtration rate (eGFR) will be calculated at day 7 and months 1, 3, 6, and 12 using the Modification of Diet in Renal Disease (4 variable – MDRD) criteria.

Calculation of C/D Ratio: Calculation of the daily trough level over the average daily total tacrolimus dose delivered either by ENVARSUS or by SOC twice a day Tacrolimus will be performed monthly throughout the study.

Patient Survival: Patient survival is any subject that is known to be alive at the study conclusion.

Graft Survival: Graft survival is defined as any subject that does not fit the following definition of graft loss: subject death, re-transplantation, transplant nephrectomy, or return to dialysis for a period of ≥6 weeks by study end. *Acute Rejection*: For study purposes, diagnoses of rejection require biopsy confirmation. Both acute cellular and antibody mediated rejection will be assessed and graded according to published criteria [Solez et al, 2008] by the NYPH

Renal Pathology Division pathologist.

Adverse Events

Adverse event collection will begin once informed consent has been signed and continue throughout the subject's participation in the study. A subset of the routine laboratory assessments obtained per SOC, including creatinine, hemoglobin, hematocrit; platelet count; white blood cell count; serum sodium, potassium, blood urea nitrogen, glucose, urinalysis (including urinary protein), tacrolimus trough concentrations.

Physical Examination

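### Randomised patients who do not start tacrolimus within 48 hours of transplant are dropped from the analysis, and no efficacy set keeps them

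*Combined protocol and SAP*

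**What the plan says.** **The rule.** The last paragraph of the Inclusion Criteria covers patients who met the criteria when randomised but were not started on Envarsus or immediate-release tacrolimus. Those not started "within 48 hours of transplant will be classified as a recruitment failure and not included in the analysis". The wording is the same for both arms, and it is not limited to any endpoint.

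**Timing.** The Study Design Overview says: "Patients will be screened prior to surgery and randomized 1:1 to receive, within 48 hours of transplantation". The Randomization section places randomisation on the day of transplant, before surgery. Footnote 2 of the Schedule of Events places it about 7 days earlier for living-donor transplants.

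**Analysis sets.** The Statistical Analysis section defines one population, for safety data: enrolled patients who received one or more doses. Its efficacy sentence names a test but no population.

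**Endpoints.** The planned size is "50 patients [25 patients in each arm". The secondary endpoints include: "Compare graft loss and death within 1 year post-transplant". The Efficacy Assessment section gives this "definition of graft loss: subject death, re-transplantation, transplant nephrectomy, or return to dialysis" (of six weeks or longer). eGFR is first calculated at day 7.

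**Recording.** The Adverse Events section says: "Adverse event collection will begin once informed consent has been signed". The section on reporting serious adverse events says: "All AEs occurring after informed consent is signed should be collected and recorded in the electronic chart".

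**The concern.** The 48-hour test is applied after randomisation, when the assigned arm is known to everyone. Whether a patient starts in time may depend on the early post-transplant course. It may also depend on supply, which differs by arm: Envarsus comes through the research pharmacy, while the immediate-release product comes from the transplanting centre during the inpatient stay. Identical wording therefore does not guarantee that removals balance in number or prognosis.

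If they do not balance, the comparisons of eGFR, rejection, graft loss and death are biased, in a direction and by an amount that the documents do not allow one to determine. For death and graft loss, the earliest events are the ones that can disappear. For eGFR, the concern is limited to surviving late starters or never-starters with a functioning graft.

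The plan also does not say whether removed patients are replaced, or whether a late starter is meant to count for safety but not for efficacy.

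**Working it through.** The plan has no figure of its own to reproduce here. It gives 50 patients, 25 per arm, with no alpha, power, effect size or SD, and it describes the study as inadequately powered. The main check is therefore a comparison of the sections. The arithmetic only gives scale.

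**1. Does the rule act after randomisation?** Yes. Both stated times of randomisation (day of transplant before surgery, or about 7 days earlier) precede a test that ends 48 hours after transplant. The label of recruitment failure cannot mean screen failure, because the sentence covers patients who were eligible when randomised.

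**2. Does any set restore these patients?**

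| Patient, as randomised | The analysis (Inclusion Criteria) | Safety set (Statistical Analysis) |
|---|---|---|
| Starts within 48 hours | in | in |
| Starts after 48 hours | out | in |
| Never starts, including death or graft loss before a first dose within the window | out | out |

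An event in the last row meets the endpoint definitions and would be recorded, because adverse events are collected from consent. It could appear at most in the adverse-event listing.

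**3. Chance that the rule removes anyone.** The per-patient miss probability p is assumed. P(at least one of 50) = 1 − (1 − p)^50.

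| p | P(at least one) | Expected removals, 50p |
|---|---|---|
| 1% | 39% | 0.5 |
| 2% | 64% | 1.0 |
| 5% | 92% | 2.5 |

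**4. Binary endpoints.** Take an arm of 25 with e events and remove one patient who had an event.
- Not replaced: e/25 − (e − 1)/24 = 4.00, 3.83, 3.67 and 3.33 percentage points for e = 1, 2, 3 and 5. With e = 1, the rate goes from 1/25 = 4.0% to 0/24 = 0%.
- Replaced by an event-free patient: e/25 − (e − 1)/25 = 4.00 points for every e.

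**5. eGFR.** Let k patients be removed from an arm, and let g be the mean of the retained minus the mean of the removed. The full-arm mean is the retained mean − (k/25)g, so the arm difference shifts by (k1·g1 − k0·g0)/25. With one common gap this is (k1 − k0)g/25. The gaps of 5 and 20 mL/min are assumed.

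| Removed, arm 1 vs arm 0 | g = 5 | g = 20 |
|---|---|---|
| 1 vs 0 | 0.2 | 0.8 |
| 2 vs 0 | 0.4 | 1.6 |
| 4 vs 1 (stress case) | 0.6 | 2.4 |

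Equal numbers do not ensure a zero shift. Two removed from each arm with gaps of 20 and 5 gives (2×20 − 2×5)/25 = 1.2 mL/min. The shift is zero if removals balance in both number and prognosis. Replacing removed patients with patients like those retained leaves the shift unchanged and restores only precision.

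**6. Against sampling error.** The 95% CI half-width is t × SD × √(1/n1 + 1/n0), with an assumed SD of 15 or 20 mL/min.
- 25 vs 25: 8.5 or 11.4
- 24 vs 25: 8.6 or 11.5
- 21 vs 24: 9.0 or 12.1

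The eGFR shifts are well inside these widths.

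**The case against.** The strongest reply is that the practical effect is small and may be nil. Starting within 48 hours is part of the assigned treatment and falls in the immediate post-transplant period. Patients who will not be maintained on tacrolimus are already excluded, and the rule is stated in advance and worded alike for both arms. The primary endpoint centres on C/D, which does not exist without a dose, so excluding never-starters costs that analysis nothing. Graft loss through dialysis needs six weeks, so only death, nephrectomy or re-transplantation could occur within the window. Such an event before any dose says little about formulation. This is an exploratory pilot, and every input to the size of the effect is assumed.

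Most of this is fair, and it limits the weight of the point. It does not remove it. The protocol still commits to comparing rejection, graft loss and death by arm, and it hopes that trends will guide a larger study. Late starters do have C/D values. Nothing in the documents shows that removals would differ by arm, but nothing protects the comparison if they do.

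Two further objections stand in part. A main set of randomised and transplanted patients is itself a restriction, and it matters more where living-donor recipients are randomised about a week before surgery. It must therefore be disclosed and the omitted patients reported by arm. Also, the discontinuation criteria do not list a missed start, but they concern stopping treatment, so they do not prove that follow-up of a never-starter continues.

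**Conclusion.** The concern holds and should be fixed. It is certain from the text that the plan removes randomised patients on a post-randomisation criterion, and that no efficacy set or sensitivity analysis keeps them. Whether bias follows is not known: it requires that some patients miss the window and that the removals differ by arm in number or prognosis. If nobody misses it, the rule changes nothing.

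Under the assumed inputs, at least one removal is quite likely. The consequence is visible for a rare binary event, at roughly 4 percentage points per patient, and modest for mean eGFR.

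**What to change.** **Main analysis.** Compare rejection, graft loss and death in all randomised and transplanted patients by assigned arm, whatever the time of first dose. State that this is a small restriction of the all-randomised set, made because the endpoints count from transplant. Report by arm anyone randomised but not transplanted.

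**eGFR.** Use the same set where eGFR can be measured, and report deaths and graft losses alongside by arm and visit. State a missing-value rule in advance. One option is observed values in patients alive with a functioning graft, plus a sensitivity analysis that ranks death or graft loss as the worst outcome.

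**C/D.** Analyse by assigned arm in patients with a trough and a dose.

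**48-hour set.** Keep it as a sensitivity analysis. Report late and absent starts by arm with reasons.

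**Clarify in the text:**
- whether the Inclusion Criteria rule applies to efficacy only
- how it relates to the safety set
- whether removed patients are replaced
- that patients who miss the window remain in follow-up

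**Cost.** Wording in the eligibility and analysis sections, plus outcome data for the few patients concerned. Those data can come from the standard-of-care visits already used (Schedule of Events, footnote 3) and the adverse-event records kept from consent. Late starters may slightly dilute the early C/D contrast.
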